***PRRT administration protocol: (in sequence)***

One day prior (Day 0)		Tablet Dexamethasone 4 mg BD oral
Day of therapy (Day 1)	Premedication	Tablet Aprepitant 125 mg oral Intravenous Dexamethasone 8 mg Intravenous Palonosetron 0.25 mg
Patient admitted	Amino Acid Infusion to be started (1 hour after pre-medication)	Intravenous infusion of lysine and arginine diluted in 500 ml of normal saline over 1 hour
	PRRT	Intravenous infusion of 145 mCi of Tb 161 DOTATATE diluted in 100 ml normal saline over 30 minutes
	After PRRT infusion is over, start amino acid infusion	Intravenous infusion of lysine and arginine diluted in 1500 ml of normal saline over 3 hours. Patient discharged
Day 2		Tablet Aprepitant 80 mg oral, in morning Oral Dexamethasone 4 mg BD
Day 3		Tablet Aprepitant 80 mg oral, in morning Oral Dexamethasone 4 mg BD

**11. Post-therapy scanning:** This involves looking at biodistribution of Tb-161 DOTATATE on post-therapy images, which are performed without any additional intervention (radiotracer injection) as Tb-161 also has gamma emission hence these images are acquired from the therapeutic tracer injection. Organ based dosimetry for tumor, kidney and bone marrow will be performed by acquiring whole body planar images at 4-, 24- and 72-hours following Tb-161 PRRT administration, on Dual head Gamma Camera in Dept of Nuclear Medicine at Tata Memorial Hospital/RRU, ACTREC. Images acquired will be processed on OLINDA XM software to calculate the target and non-target absorbed doses.

**12. Discharge and Follow-up:** After the post therapy scanning, patients will be discharged with summary document containing information about patient details, treatment received and advice at discharge, duly signed by Nuclear Medicine Physician authorized for the same. This is the standard practice in keeping with the radiation safety guidelines.

**Advice at discharge:** There are no specific precautions to be followed with respect to radiation safety.

**Follow up:** Patients will be followed up while on active treatment with cancer directed therapy as well as supportive care.

- a.** Clinical and serological investigations like CBC, LFT, RFT, serum electrolytes will be done at 2 weeks, 4 weeks and at 6 weeks after each therapy session.
- b.** After the completion of 2 sessions, participants will be followed up as per current standard institutional protocol as follows;
- c.** Clinical and Quality of Life Assessment using EORTC QLQ C30 questionnaire before therapy, at 4 weeks and 8 weeks after each therapy session.
- d.** Imaging Follow-up (as per established institutional standard-of-care) as follows: Ga-68 DOTANOC PET/CT will be performed at 4-6 weeks after each therapy session for documentation of response. After completion of protocol treatment, patients will be followed up as per standard institutional practices.

**13. Study Duration:** 2 years

**14. Follow-up Period:** 1 year

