#### **9. Exclusion criteria**

- Serum creatinine level of more than 1.6 mg/dl or a creatinine clearance of less than 50 ml/min
- Hemoglobin level of less than 8.0 g per deciliter
- Red blood cell count less than 300,000/cubic millimeter
- White cell count of less than 2000 per cubic millimeter
- Platelet count of less than 75,000 per cubic millimetre
- Total bilirubin level of more than 3 times the upper limit of the normal range
- Serum albumin level > 3.0 g/dl
- Pregnancy and Lactation
- Patients with concurrent malignancies

**10. Study Methodology:** Patients referred from Neuroendocrine tumor clinic fulfilling the inclusion and exclusion criteria will be enrolled in the study for treatment with Terbium-161 DOTATATE. Since the physical characteristics of Tb-161 are same as Lu-177 and since the peptide is same (DOTATATE), principles and procedure of treatment is same as Lu-177 DOTATATE PRRT. This is a day care therapy and the patient shall be admitted and discharged on the same day. Patients will be administered 2 cycles of Tb-161 PRRT at intervals of 8-12 weeks. Pre-therapy investigations will be as per 'standard of care' work-up for PRRT. Even the therapy administration protocol will be same, which will be as follows:

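### The discharge advice in section 12 rules out radiation-safety precautions without qualification, although patients go home the same day after 145 mCi of a gamma-emitting nuclide

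*Protocol*

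**What the plan says.** Protocol section 12 describes the discharge document as covering "treatment received and advice at discharge, duly signed by Nuclear Medicine Physician authorized for the same". It adds that this is standard practice and consistent with radiation safety guidelines, without naming any. The heading for the advice itself follows, and its whole content is "There are no specific precautions to be followed with respect to radiation safety".

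Three other places describe the patient to whom this applies:

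- **Section 10, text:** "This is a day care therapy and the patient shall be admitted and discharged on the same day".
- **Section 10, administration table:** "Intravenous infusion of 145 mCi of Tb 161 DOTATATE diluted in 100 ml normal saline over 30 minutes".
- **Section 11:** "Tb-161 also has gamma emission hence these images are acquired from the therapeutic tracer injection". Whole-body images are planned at 4, 24 and 72 hours.

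On the time of discharge, the table marks it in the same cell as the last amino acid infusion, which is "diluted in 1500 ml of normal saline over 3 hours". Section 12 instead says "After the post therapy scanning, patients will be discharged with summary document".

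**The concern.** The sentence is a positive instruction in the protocol, so it is not a detail left for another document to supply. It has no qualifier: it does not say that nothing is needed beyond usual practice, or that nothing is needed once a release criterion is met. A site member who follows it literally has no reason to give advice on close contact, hygiene or excreta.

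The protocol's own description points the other way. The patient leaves within hours of receiving a therapeutic activity, and radiation from that activity is expected to be detectable outside the body for at least three days. Those affected by a literal reading are the patients and the people around them. The statistical design is not involved.

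**Working it through.** The main point rests on text, and the protocol states no figure to reproduce. The first three steps set the relevant statements side by side. The last two are simple arithmetic.

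**1. Does anything qualify the sentence?**

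| Place in the Protocol | What it offers | Does it qualify the advice? |
|---|---|---|
| Section 12, sentence before the advice | General reference to radiation safety guidelines, attached to discharge with a signed summary | No. It names no guideline and gives no release criterion |
| Section 1, Current Indian scenario | Approval obtained from the Atomic Energy Regulatory Board (AERB) | No. It states no discharge conditions |
| Section 10 | "principles and procedure of treatment is same as Lu-177 DOTATATE PRRT" | Not expressly. It concerns treatment, and section 12 does not refer back to it |

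**2. Do the protocol's facts support the sentence?** Section 11 relies on emission from the administered dose being measurable outside the body at 4, 24 and 72 hours. At least the last two times fall after a same-day discharge. The visible text gives no retained activity, dose rate or release limit from which one could conclude that precautions are unnecessary.

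**3. Can the exposure be quantified?** No. A contact dose would need a dose rate at a distance, clearance data and contact times, and the protocol gives none of these.

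**4. How many discharges are covered?** Section 16 plans at most 20 patients and section 10 plans 2 cycles: 20 × 2 = 40 at most. If the trial stops after stage 1, the figure is at most 6 × 2 = 12. Both are upper limits, because section 15 withholds the second session after progression or after complete response.

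**5. When does discharge take place?** Assume no gap between infusions and discharge as soon as the last one ends.

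- Table, from the start of the Tb-161 infusion: 0.5 h + 3 h = 3.5 h. From its end: 3.0 h.
- First scan at 4 h, if counted from the start: 4.0 − 3.5 = 0.5 h after the table's discharge. If counted from the end: 4.0 − 3.0 = 1.0 h after it.
- From premedication, table discharge falls at 1 + 1 + 0.5 + 3 = 5.5 h. The 4-hour scan falls at 1 + 1 + 4 = 6.0 h or 1 + 1 + 0.5 + 4 = 6.5 h.

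The table therefore discharges the patient before any scan, whereas section 12 discharges after scanning. Waiting for all the scans would mean 72 hours and would contradict day care. Discharge after the 4-hour scan reconciles the statements.

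**The case against.** The strongest reply is that the sentence is loosely worded but harmless. It follows directly on a reference to radiation safety guidelines, the department reports regulatory approval, and the hospital reports nearly 700 cycles of Lu-177 PRRT since 2019. Section 10 treats the Tb-161 procedure as identical to the Lu-177 one. Read together, these suggest that the authors meant nothing beyond existing practice. The summary is also signed by an authorised physician, and the protocol does not say that the sentence is copied into it. Patient-facing advice may sit in the consent pages, which are not shown.

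Much of this stands. It would be wrong to say that the protocol offers no basis at all, since it gives two general references. The milder reading is plausible. What patients are actually told cannot be known from this document.

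The reply does not rescue the wording. The general references contain no criterion, section 12 does not state the milder meaning, and the protocol does not describe Lu-177 discharge advice. If the consent pages do list precautions, they would conflict with section 12 as written.

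**Conclusion.** The point holds as a defect in a stated instruction. Section 12 dismisses radiation-safety precautions without qualification, and the protocol's account of same-day release after 145 mCi of a gamma emitter does not support that.

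A reader might infer that patients are released unsafely, that a regulatory limit is breached, or that the sites give no advice in practice. The document supports none of these. It contains no dose rate, limit or clearance figure and does not show the sites' discharge instructions.

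The reach is at most 40 discharges, and the dose consequence is unknown. The discharge-time mismatch of 0.5 to 1.0 h is real, but it is only a matter of consistency and says nothing about exposure. The primary endpoint, decision rule and sample size are untouched. The conclusion rests on the visible text alone. I would class it as a cheap patient-safety improvement of low priority.

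**What to change.** Delete the sentence under the discharge-advice heading in section 12 and put in its place: *Patients will receive written radiation-safety instructions at discharge (close contact, hygiene and excreta), in line with the site's AERB-approved practice for PRRT.*

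Naming the topics matters. A bare pointer to the Lu-177 instructions, which are not shown, could leave the position unchanged. The protocol does not say what the AERB approval covers, so the sponsor should confirm that the reference to it is accurate for both sites. A dose-rate measurement at discharge may be cited if the sites already make one, but this change does not require it.

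As a minor consistency edit, state in the section 10 table and in section 12 that same-day discharge follows the 4-hour scan, with the 24- and 72-hour scans as return visits.

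The cost is one replaced sentence, one aligned discharge time, a few minutes of instruction per patient and a discharge about 0.5 to 1 hour later. Day care is kept, and nothing in the design or analysis changes.

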**15. Study Assessments:**

**Response assessment:** Disease control rate will be measured as a primary endpoint. It is percentage of patients achieving complete or partial response or stable disease on Ga-68 DOTATATE PET/CT. Response assessment will be done using RECIST 1.1 for solid tumors. Non-PD (non-disease progression) after one session of Tb-161 therapy will be eligible for the second session. Patients showing CR with no

residual measurable disease will not undergo a second session of therapy. Patients with PD after 1 cycle of Tb-161 DOTATATE therapy will not continue in the study and will be referred to NET Clinic for further management. Currently there is no standard of care for treatment of refractory NET.

**Safety Assessment:** At each visit, the investigator will evaluate the subject to determine whether any AEs have occurred. CBC, LFT, RFT, Serum electrolytes will be done at 2 weeks, 4 weeks and 6 weeks after each therapy. AEs may be directly observed, reported spontaneously by the subject or by questioning the subject at each study visit. All laboratory values will be evaluated by the Investigator as to clinical significance. All post-baseline abnormal laboratory values considered clinically significant by the Investigator will be recorded as an AE. The NCI Common Terminology Criteria for Adverse Events version 5 (NCI CTCAE v5.0) will be used to classify and grade the intensity of adverse events during and after each treatment cycle. CTCAE will be used to grade all events regardless of attribution, in order to ensure objective reporting, and in order to report trial data according to accepted international guidelines. The highest grade of each observed toxicity will be recorded. The results will be computed in a tabular form in which the proportion of people having their highest grade of toxicity will be charted.

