**Secondary:**

- To assess the safety profile expressed in terms of incidence of >grade 3 toxicity or proportion of patients developing > grade 3 in metastatic neuroendocrine tumors who have progressed on Lu-177 DOTATATE PRRT.

**3. Study End-point:** Safety and efficacy assessment**4. Study Design:** Phase II (Simon Two Stage), Interventional, Single Arm, Open Label**5. Study Sites:** Departments of Nuclear Medicine, TMH, Parel and RRU, ACTREC**6. Pre-screening:** Patients of metastatic NET who have progressed on Lu-177

DOTATATE PRRT will be referred after discussion in Neuroendocrine Tumor Clinic, TMH or HPB-UGI Clinic at RRU, ACTREC.

**7. Screening:** Patients will be confirmed for disease progression on Ga-68 DOTATATE and/or FDG PET/CT imaging.**8. Inclusion Criteria:**

- Male or female, age greater than 18 years
- Histopathological diagnosis of well-differentiated GEP-NET
- Positive Ga-68-DOTANOC PET/CT, Krennigs score  $\geq 3$
- Locally advanced/inoperable disease or metastatic disease
- Patient who have shown disease progression with Lu-177 DOTATATE PRRT

- Karnofsky performance-status score of at least 60 or ECOG performance status </=2
- Life expectancy greater than 6 months

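### Laboratory toxicity is recorded at the investigator's discretion and charted at its worst grade with no reference to the pre-treatment grade, so cytopenia present at entry can be counted as toxicity on Tb-161, or real worsening left out

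*Protocol*

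**What the plan says.** Section 15 of the protocol (Study Assessments, Safety Assessment) sets out how laboratory toxicity is handled:

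- Entry into the record: "All post-baseline abnormal laboratory values considered clinically significant by the Investigator will be recorded as an AE".
- Grading: "CTCAE will be used to grade all events regardless of attribution", using CTCAE version 5.
- Summary per toxicity: "The highest grade of each observed toxicity will be recorded".
- Presentation: a table in which "the proportion of people having their highest grade of toxicity will be charted".

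The only secondary objective in section 2 is "To assess the safety profile expressed in terms of incidence of >grade 3 toxicity", or the proportion of patients affected.

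On the population, section 8 requires "Patient who have shown disease progression with Lu-177 DOTATATE PRRT". The blood-count exclusions in section 9 cover haemoglobin (below 8.0 g/dl), red cells, total white cells ("White cell count of less than 2000 per cubic millimeter") and platelets ("Platelet count of less than 75,000 per cubic millimetre"). Neither neutrophils nor lymphocytes are listed. Section 10 leaves the pre-therapy tests to the standard work-up for PRRT and does not link them to toxicity grading.

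**The concern.** None of the four steps in section 15 compares a grade with the grade before treatment or requires worsening. A post-baseline value need only be abnormal and be judged significant. In patients who have all had another radionuclide therapy, a low count seen after Tb-161 may have been just as low before it.

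The entry criteria do not close this gap for the two cell lines that matter most here. A total white count of 2000 or more does not rule out a low neutrophil or lymphocyte count, because one can be low while the other makes up the total. Lymphopenia is also the severe cytopenia that the protocol expects most often: 9%, against 1% for neutropenia and 2% for thrombocytopenia.

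The investigator's judgement acts in both directions. An unchanged low count may or may not be recorded, and a real fall may be passed over as not significant. Section 15 says that CTCAE grading is there to make reporting objective, but it is applied only to values that have already passed an unblinded, subjective filter. With no control arm, comparison with baseline is the main way to separate old damage from new. What is at stake is the interpretation of the only secondary objective, in a trial whose aim names safety beside efficacy.

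**Working it through.** The protocol derives no figure from this rule, so there is none to reproduce. The check is a reading of the text followed by an illustration of size.

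**Reading.** Consider a patient with grade 4 lymphopenia before cycle 1 and the same grade at weeks 2, 4 and 6.

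1. The value is post-baseline and abnormal. If it is judged significant, it is an adverse event of grade 4, is the highest grade, and enters the table and the endpoint.
2. If it is judged not significant, it is not recorded at all.
3. Section 15 gives no criterion for choosing between these outcomes. A patient who truly worsens faces the same choice.

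**Inputs for the illustration.**

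- Rate of grade 3 or 4 lymphopenia: 9% (section 15). It is treated here as new-onset, which the protocol does not state.
- Rate of grade 3 or 4 neutropenia: 1% (section 15), treated in the same way.
- Maximum sample size: 20 (section 16).
- Share q entering with that grade: not in the documents, assumed to be 0%, 5%, 10% or 20%.
- All carried-over values are recorded, and entry status is independent of new toxicity (assumptions).

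**Formula.** Apparent rate = 1 − (1 − q)(1 − new rate).

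Lymphopenia:

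- q = 0: 1 − 1 × 0.91 = 9.0%
- q = 0.05: 1 − 0.95 × 0.91 = 13.6%
- q = 0.10: 1 − 0.90 × 0.91 = 18.1%
- q = 0.20: 1 − 0.80 × 0.91 = 27.2%

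| Assumed q | Apparent lymphopenia | Expected of 20 | Chance of 4 or more of 20 | Apparent neutropenia | Expected of 20 |
|---|---|---|---|---|---|
| 0% | 9.0% | 1.8 | 0.10 | 1.0% | 0.2 |
| 5% | 13.6% | 2.7 | 0.28 | 6.0% | 1.2 |
| 10% | 18.1% | 3.6 | 0.50 | 10.9% | 2.2 |
| 20% | 27.2% | 5.4 | 0.84 | 20.8% | 4.2 |

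The chances in the fourth column are exact binomial tails with 20 patients.

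**Effect of the filter.** If only a share f of carried-over cases is recorded, q is replaced by f × q, so the apparent rate lies between 9% and the tabulated value. If only a share g of new cases is recorded, 9% is replaced by g × 9%, which pulls the rate down. The protocol fixes neither f nor g, so even the direction of the net error is undetermined.

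**Effect of the grade threshold.** The table above concerns grades 3 and 4 together. The objective in section 2, read literally, starts above grade 3. The protocol does not split its 9% into grade 3 and grade 4, so no corresponding figure can be computed for the literal endpoint. Only a carried-over grade 4 would enter it; a carried-over grade 3 would appear in the section 15 table alone.

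**The case against.** The strongest reply is that tabulating the worst grade from any cause is an ordinary and conservative choice in a single-arm trial. Treatment-emergent definitions and shift tables usually belong in the statistical analysis plan, which was not available for this review. That is fair as far as it goes, and the mere absence of a shift table would not be a finding. But section 15 does not leave the matter open. It fixes the filter, the grading and the summary itself, and an analysis plan that counted only worsening would depart from the table that it prescribes. Nothing in it prevents a baseline comparison from being shown alongside, which is why an addition is enough.

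Several stronger readings are tempting, and the documents do not support them:

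- *Earlier cytopenia is always counted.* It can be. The investigator may leave out an unchanged value.
- *Patients enter with cytopenia caused by Lu-177.* The protocol gives no data on entry counts. At 0% there is no carry-over, although the discretionary filter remains.
- *The table attributes each event to Tb-161.* Grading whatever the cause makes it an all-cause table. The difficulty is that, without the baseline grade, a reader cannot tell new events from old ones.
- *Every blood count is equally exposed.* The haemoglobin, white-cell and platelet limits in section 9 restrict carry-over of severe grades. The point is mainly about lymphocytes and neutrophils.
- *The safety result as a whole is unreliable.* The endpoint is secondary and descriptive, and no test or safety stopping rule is attached to it.

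It is also true that 9% may already be an all-cause worst-grade rate. In that case it is not a clean starting value, and the illustration would overstate the contrast.

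**Conclusion.** The point holds in a limited form. Section 15 fixes a rule under which laboratory cytopenia present before Tb-161 can be counted as toxicity on it, and true worsening can be omitted, with nothing but unblinded judgement to decide. This follows from the text and needs no assumption.

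The size does need assumptions. An assumed 10% entry prevalence of grade 3-4 lymphopenia, fully recorded, would double the apparent rate from 9% to 18%; the assumed range of 0% to 20% gives 9% to 27%. These figures illustrate sensitivity in a sample of 20 and are not estimates of bias in this trial. On the literal threshold of the secondary objective, the effect on the endpoint is confined to grade 4 and cannot be quantified.

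The primary endpoint, the two-stage rule and the sample size are untouched. The change is worth making before data collection because it makes the only secondary objective depend less on judgement and on what patients bring with them.

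**What to change.** In section 15:

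1. Grade every scheduled CBC (with differential), LFT, RFT and electrolyte value directly by the CTCAE v5.0 numeric limits, whether or not the investigator considers it significant.
2. Record the grade of each parameter before cycle 1.
3. Report the proportion of patients whose grade worsened from that baseline, with a table of baseline grade against worst grade. Keep the all-cause worst-grade table beside it, and show each grade separately so that the result can be read at either threshold.

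The cost is some wording and slightly more tabulation. Blood tests at 2, 4 and 6 weeks after each session are already scheduled, and a pre-therapy work-up exists. Since section 10 does not list its contents, the investigators should confirm that it includes a differential count and electrolytes, and that the follow-up CBC includes a differential. No change to eligibility, treatment, the primary analysis or the sample size is needed.
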